#### 5.5. **Follow-up Safety Period**

A 14-day follow-up safety and cDFU evaluation visit will be scheduled for all study subjects and will include assessments as per the Schedule of Events and as detailed above for V8.

#### 5.6. **End of Study Definitions**

The end of the study is defined as the date of the last visit of the last subject in the study or last scheduled procedure shown in the Schedule of Events for the last subject in the trial. Sponsor retains the right to terminate the study at any time in accordance with all guidance and state and federal laws.

# 5.7. Scientific Rational for Study Design

One of the most important goals of this study is to identify the Recommended Phase 2b Dose (RP2D)/MTD with acceptable dose-limiting toxicity of the new drug. Among all dose-finding methods used in clinical studies, this design is the most standard approach used.

# **5.8.** Justification for Starting Dose

The rationale for initial dose concentration selection is based on non-clinical data obtained from the 28-day toxicology results in Rats.

# 5.9. Study Oversight Committee

The decision whether to dose escalate-or-not to the next higher concentration, e.g., 10% Nu-3 gel will be based on the recommendation of the DMC review of all safety data from the previous subject cohort. This decision will be based on pre-defined Dose Limiting Toxicity criteria (DLT), which will be detailed in the DMC Charter. Details regarding the DMC's responsibilities will be outlined in a separate charter.

# 6. STUDY POPULATION

#### **Inclusion criteria**

- 1. Men and women at least 18 years of age and up to 80 years of age, inclusive.
- 2. Voluntary written consent, given before performance of any clinical investigation-related procedure, and with the understanding that consent may be withdrawn at any time without prejudice to future medical care
- 3. Non-hospitalized ambulatory subjects suffering from diabetes mellitus, Type I or II per ADA criteria
- 4. The target ulcer is classified as grade 1 ulcer according to a Wagner Scale. These ulcers are superficial, full-thickness ulcers limited to the dermis, not extending to the subcutis.
- 5. Target ulcer is between 2 and 10 cm2 post debridement at screening and baseline.
- 6. The target ulcer must be no higher than the ankle (on or below the malleolus (ankle bone) with  $\geq 50\%$  below the malleolus.
- 7. Presence of a persistent cDFU for at least 4 weeks and not more than 1 year that has failed to respond to standard of care
- 8. Adequate vascular perfusion as evidenced by one of the following
  - a. Dorsal transcutaneous oxygen measurement (TCOM) or a skin perfusion pressure (SPP) measurement of ≥ 40 mmHg
  - b. Ankle Branchial Index (ABI) between 0.7 and 1.3 within 3 months of Screening using the extremity with the target ulcer
  - c. Arterial Doppler ultrasound evaluating for biphasic or triphasic dorsalis pedis and posterior tibial vessels at the level of the ankle or a TBI (Toe Brachial Index) of > 0.6 is acceptable
- 9. Subject has a caregiver who is able to attend baseline visit and apply wound treatment and study dressings for the study duration
- 10. Subject completed protocol-defined standardized wound care during the Screening and Run-in periods leading up to Day 0.
- 11. Must meet one of the following criteria:
  - a. Female subjects of Non-Child-Bearing Potential defined as:
    - i. Postmenopausal for at least 1 year, or surgically sterilized (i.e., hysterectomy or bilateral oophorectomy more than 3 months prior to Screening), or
    - ii. Bilateral tubal ligation more than 6 months prior to Screening
    - iii. Must have a negative serum  $\beta$ -hCG pregnancy test at screening and not be breastfeeding prior to being administered with the study drug.
  - b. Male subjects of Non-Childbearing Potential defined as those vasectomized subjects whose vasectomy was performed 6 months prior to Screening or those diagnosed as sterile by a physician.
  - c. Females and Males of Childbearing Potential who practice an acceptable method of contraception defined as the use of any form of hormonal contraceptive, a barrier method with spermicide, condoms, intrauterine device, or abstinence from sexual intercourse starting at least 60 days prior to Screening and continuing at least 30 days following the last treatment.
- 12. Subjects must be willing to undergo all clinical investigation-related procedures and attend all required visits.

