#### Randomization:

Randomization will be conducted to a ratio of 3:1 (active: placebo). All qualified subjects will be enrolled and randomized in two sequential Cohorts of 16 each, Cohort 1 to either Nu-3 gel at 5% or to placebo gel, and Cohort 2 to either 10% Nu-3 gel or to placebo gel. The two cohorts will be enrolled sequentially, each with 12 active and 4 placebo subjects, and safety will be evaluated by the independent Data Monitoring Committee (DMC) before proceeding to the next Cohort. At the completion of Cohort 2, the DMC will review all data and make a recommendation as to the appropriate dose for the next study.

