#### **Exclusion criteria**

- 1. Ulceration with exposed tendon, capsule, or bone
- 2. Suspicion of bone or joint infection by clinical or other criteria

- 3. Unable or unwilling to utilize the standardized offloading RCW as required per protocol.
- 4. Target ulcer has decreased in area by ≥30% between Screening (V1) and Baseline (V3) visits
- 5. Any subject that is currently on/requires oral, systemic or topical antibiotics, or is anticipated to require use during the course of the trial
- 6. Any subject that has vascular compromise requiring surgical intervention or has undergone vascular reconstruction or angioplasty less than 1 month prior to randomization. Any planned surgical procedures during the study participation
- 7. Serum Creatinine level >3.0 mg/dL
- 8. Hemoglobin A1c (HbA1c) >12%
- 9. Aspartate Aminotransferase (AST, GOT) and/or Alanine Aminotransferase (ALT, GPT) >3x the upper limit of normal
- 10. Acute active Charcot foot
- 11. The target ulcer is within 3 cm of any other ulcer.
- 12. Any subject that would be unable to safely monitor the infection status at home, and return for scheduled visits
- 13. History of immunosuppression or taking immunosuppressive agents including systemic corticosteroids, except stable daily doses of 5 mg/day or less for chronic conditions
- 14. Any subject with a life expectancy  $\leq 6$  months
- 15. Pregnancy, including a positive pregnancy test at Screening or Baseline, or lactation
- 16. Use of investigational drugs within 28 days prior to screening
- 17. History of concurrent condition that, in the Investigator's opinion, would jeopardize the safety of the subject or compliance with the protocol
- 18. Likely inability to comply with the protocol or cooperate fully with the investigator and site personnel
- 19. Known or suspected active abuse of alcohol, narcotics, or non-prescription drugs
- 20. Prior randomization in this clinical trial, or a previous Bisphosphocin study

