# 7.4. Method of Treatment Assignment

All subjects will be centrally assigned to randomized study treatment using an automated system. Before the study is initiated, directions for use will be provided to each site.

Returned study treatment should not be re-dispensed to the subjects.

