# **Brief Trial Description**

This study is a phase 2a, multi-center, double-blind, placebo-controlled, dose-escalating, parallel group, randomized controlled trial designed to evaluate the safety and tolerability of topically applied bisphosphocin NU-3 gel to clinically non-infected Wagner grade 1 diabetic foot ulcers (DFUs).

Two weeks after screening, subjects will be randomized 3:1 to bisphosphocin Nu-3 gel and standard of care (SOC) or placebo gel and SOC to treat Wagner 1 DFUs. Major inclusion criteria will be DFUs between 1.0 and 10 cm^2 initial area and having no wound ischemia.

Subjects will be seen weekly until 6 weeks after randomization unless the subject's wound healed, or the subject is withdrawn or lost to follow-up (i.e., early termination). The bisphosphocin Nu-3 or placebo gel will be applied starting on the day of randomization for 4 weeks twice daily. The study will be executed in two phases: cohort 1 and cohort 2, in which the doses for the intervention group will be 5% or 10% Nu-3 gel.

SOC in this study will be offloading of the DFU using a removable cast walker provided to the subject, appropriate sharp or surgical debridement (note: there will be several rules pertaining to prohibition on certain visits and degree of debridement), and infection management post-randomization as deemed appropriate by the investigator. Primary dressings will be Mepitel (or equivalent), Tegaderm, and padding/Coban Lite 2- layer dressing.

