#### **Sample Size Calculations**

Since this is a pilot study focusing primarily on safety, no sample size calculations will be done. Based on general experience with phase 2a trials, it is planned to enroll 32 subjects (24 active and 8 placebo).

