## Randomization

Subjects eligible for the study after screening and run-in will be randomized 3:1 to bisphosphocin Nu-3 gel and SOC or placebo gel SOC.

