  - Laboratory evaluations and vital signs assessments will be summarized by dose group (including placebo group) and time point of collection (i.e., visit number starting with randomization visit) (see shell Table 2).
    - Tables will also be constructed for each subject per timeline (see Shell Table 3)

[figure not shown]
SAP: LLA-Nu3-CLIN002 Page 8 of 21

 Table describing change in value and percentage change from baseline for each visit will be provided for vital signs for each subject (see Shell Table 4)

- Table describing out-of-normal range shifts will be provided for clinical laboratory results for each subject, grouped according to dose group (See Shell Table 5)
- Table describing changes noted in physical examinations (at each visit after randomization) will be constructed for each subject, grouped according to dose group (see Shell Table 6)
- Efficacy date will be analyzed as follows:
  - Summary statistics of DFUs that healed by treatment group by 6 weeks (numbers and percentage healed); graph showing weekly percentage of wounds healed by treatment group
  - PAR weekly plot by treatment group; summary table of PAR values by week and treatment group
  - Time to heal within 6 weeks (summary time to heal statistics by treatment group) using Kaplan-Meier method; probability of wound healing (1-survival ≡ 1-wounds not healed) plot by treatment group. If the percentage healed figures for the 5% and 10% Nu-3 groups at 6 weeks is within 10% and a statistical power calculation shows that the proportions of wounds healed for the combined versus placebo groups is at least 80%, the times to heal will be tested using the logrank test.
  - Bacterial counts (CFU/g) for weeks 0-4 will be analyzed by (a) reporting the means and standard deviations for each group at each time point and (b) using GLMM (general linear modeling with repeated measures [weeks 1-4] and counts at week 0 as a factor)
  - Microbiological data will be summarized for each of the 3 treatment groups for each visit (visits 1, 3, 4, 5, 6, 7; unscheduled visit; early termination) as follows (a) list of species detected in each microbiological sample (Shell Table 11); and (b) susceptibility testing to the following drugs for each microbiological sample: penicillin, vancomycin, and linezolid (Shell Table 12)
    - \*A reason will be given in each instance in which susceptibility testing was *not* done (e.g., no growth).

SAP: LLA-Nu3-CLIN002 Page 9 of 21

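### Day 28 percentage area reduction is summarised by arm without using baseline ulcer area or run-in area change, both already collected; a supportive adjusted estimate should be pre-specified

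*Protocol*

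**What the plan says.** - **Entry size.** Protocol Section 6, inclusion criterion 5: "Target ulcer is between 2 and 10 cm2 post debridement at screening and baseline". The SAP's Brief Trial Description gives another range: "Major inclusion criteria will be DFUs between 1.0 and 10 cm 2 initial area".
- **Run-in change.** Protocol Section 6, exclusion criterion 4, removes a subject if "Target ulcer has decreased in area by ≥30% between Screening (V1) and Baseline (V3) visits". The change must therefore be worked out for every subject. It appears neither in the SAP's list of baseline variables nor in Shell Table 7.
- **Allocation.** Protocol Section 7.4: "All subjects will be centrally assigned to randomized study treatment using an automated system". SAP, Randomization: "Subjects eligible for the study after screening and run-in will be randomized 3:1". Neither names a stratification factor. The protocol synopsis adds: "The two cohorts will be enrolled sequentially, each with 12 active and 4 placebo subjects". The SAP shells have one column for 5%, one for 10% and one for placebo, so the two placebo groups are pooled.
- **Outcome.** The SAP defines PAR as (A1 − A2)/A1 × 100, where A1 is the area at randomisation. The planned analysis is "PAR weekly plot by treatment group; summary table of PAR values by week and treatment group", with no covariate. In the same list, the repeated-measures model for bacterial counts does include the week 0 count.
- **What is already reported.** Initial area is among the baseline variables to be compared between groups, and Shell Table 7 shows wound area by arm.
- **Testing.** The only planned test of a wound outcome is a log-rank test of the combined active groups against placebo. It is run only if the healed percentages in the two dose groups are within 10% of each other and a power calculation reaches 80%.

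**The concern.** Clinical effect on the ulcer and support for the dose range are secondary objectives, and after Cohort 2 the DMC reviews all data before recommending a dose for the next study. Escalation and the maximum tolerated dose rest on safety, but the PAR table will also be read. With 8 placebo subjects and 12 per dose, the arms can easily differ in starting size or in how the ulcers behaved under standard care. An unadjusted PAR difference carries whatever part of that imbalance is related to PAR. Seeing an imbalance in a baseline table does not correct for it, and an adjustment chosen after unblinding is open to challenge. The SAP already accepts the principle for bacterial counts, so leaving it out for PAR looks like an oversight.

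**Working it through.** **1. The plan's own figures.** Two cohorts of 16 give 32 subjects: 2 × 12 = 24 active and 2 × 4 = 8 placebo. The analysis groups are 12, 12 and 8. The documents give no power or sample size calculation to reproduce. The protocol's entry range is 10/2 = 5-fold.

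**2. How often baseline area will be unbalanced.** In SD units, the SE of a difference in means is √(1/n₁ + 1/n₂).

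| Comparison | SE (SD units) | z for a 0.5 SD gap | P(gap ≥ 0.5 SD, either direction) |
|---|---|---|---|
| 12 v 8 | √(1/12 + 1/8) = 0.456 | 1.10 | 27% |
| 24 v 8 | √(1/24 + 1/8) = 0.408 | 1.22 | 22% |

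About half of each figure has placebo on the unfavourable side (14% and 11%). This uses a normal approximation and treats allocation as random across all 32 subjects, which is not strictly true with sequential cohorts.

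In cm², assuming areas uniform on 2–10: SD = 8/√12 = 2.31, so the 12 v 8 SE is 2.31 × 0.456 = 1.05 cm². A gap above 1 cm² in either direction then has probability 34%.

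**3. Does dividing by baseline area make PAR independent of it?** Not in general. Assume a circular ulcer whose edge advances 0.10 cm/week for 4 weeks, that is 0.40 cm. The radius is √(A/π).

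- 2 cm²: radius 0.798 → 0.398 cm; PAR = 1 − (0.398/0.798)² = 75%.
- 10 cm²: radius 1.784 → 1.384 cm; PAR = 1 − (1.384/1.784)² = 40%.

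The same edge speed gives PAR values 35 points apart at the ends of the entry range. In simulation of this model (edge speed mean 0.12–0.16, SD 0.06–0.08 cm/week, with the run-in exclusion applied), each extra cm² lowers Day 28 PAR by about 3–4 points.

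**4. What adjustment for area would do.** The documents give no correlation r between area and PAR, so a range is shown. A 0.5 SD gap in area shifts PAR by r × 0.5 SD, and the adjusted 12 v 8 SE is about 0.456 × √(1 − r²).

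| Assumed r | Shift removed | SE after adjustment |
|---|---|---|
| 0 | 0 | 0.456 SD |
| 0.3 | 0.15 SD | 0.435 SD |
| 0.5 | 0.25 SD | 0.395 SD |

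**5. Adding run-in change.** In simulations of the edge-speed model, log area alone cut the variance of the PAR difference by about 1–8%. With run-in change added, the result ran from a 1% loss to about a 30% cut, depending on the assumed correlation between run-in and treatment healing. One set gave a 10–18% cut at a correlation of 0.6, and between a 1% loss and a 5% cut at 0.3. The documents support no particular value.

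**6. The entry-range conflict matters for size.** Under the protocol's 2–10 cm², geometric mean areas differ by 1.25-fold or more (12 v 8, either direction) in about 26–30% of simulated trials. Under the SAP's 1.0–10 cm² the figure is 41–47%. The ranges span uniform and log-uniform areas.

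**The case against.** The strongest reply is that this is a 32-subject safety pilot. PAR is a plot and a table with no test, it is already scaled to baseline area, and wound area by arm will be in Shell Table 7, so a careful reader would see an imbalance. All of that stands, and it limits the point to how the estimates are read. It does not make the adjustment unnecessary, because step 3 shows that scaling leaves a dependence on area, and run-in change is not tabulated at all.

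A second reply is that V1–V3 change is a poor measure of healing tendency. Sharp debridement is required at V1 and permitted at V2, and area is measured after debridement, so the change partly reflects how much tissue was cut. That is fair, and it is why the precision gain may be near nil.

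Stronger readings are tempting, and the documents do not support them:

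- **That chance imbalance would pass as a dose effect in a test.** The conditional log-rank test compares combined active with placebo, so it cannot show one. In simulations with no drug effect (healing rates and area effects assumed), the unadjusted log-rank rejected in 3.9–5.0% of trials, and in 0.2–0.5% under the SAP's full rule. Nothing is inflated.
- **That differences between 5% and 10% are chance imbalance.** Those cohorts are enrolled one after the other, so that contrast is not randomised, and half of the pooled placebo group belongs to the other cohort for each dose. Covariates address this only in part.
- **That the log-rank test should be stratified by size.** Eight placebo subjects leave about four in each of two strata. At an assumed 20–35% healing, 32 subjects yield only about 6–11 events. This is a debatable trade, and it is not recommended here.

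**Conclusion.** The point holds as a gap in the descriptive efficacy analysis. Baseline area and run-in change are collected in every randomised subject, no size stratification is stated, and the SAP uses neither value when it summarises PAR. A randomisation specification outside these documents could contain a stratification factor. A baseline gap of 0.5 SD or more is common, at about 27% for 12 v 8 in either direction, and would shift the PAR difference by 0.15–0.25 SD if area correlates with PAR at 0.3–0.5. The 27% is arithmetic under random allocation. The shift rests on an assumed correlation, and the edge-speed results rest on circular ulcers closing at constant speed. The safety objective is not affected. The separate conflict between the 2–10 and 1.0–10 cm² entry ranges is a matter of fact and must be reconciled whatever view is taken of adjustment.

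**What to change.** 1. In the SAP's Analysis section, keep the raw PAR plot and weekly table. Add, labelled as supportive, the Day 28 PAR difference of each dose versus placebo with a 95% CI from a linear model with log V3 area and V1–V3 percent change in area as covariates. Use the same population and missing-data rule as the raw summary.
2. Add V1–V3 percent change in area to Shell Table 7.
3. State beside the estimates that 5% v 10% is a comparison of sequential cohorts, which the covariates do not make randomised.
4. Reconcile the entry range in the SAP's Brief Trial Description with inclusion criterion 5 of the protocol.

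This is SAP wording only, to be settled before database lock, with no new data or visits. The model spends two degrees of freedom: 32 − 3 = 29 residual without covariates, 27 with them. If run-in change predicts weakly, the interval will be about as wide as without it. The estimate will then still have been corrected, as pre-specified, for the area-related part of any imbalance.

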#### **Exclusion criteria**

- 1. Ulceration with exposed tendon, capsule, or bone
- 2. Suspicion of bone or joint infection by clinical or other criteria

- 3. Unable or unwilling to utilize the standardized offloading RCW as required per protocol.
- 4. Target ulcer has decreased in area by ≥30% between Screening (V1) and Baseline (V3) visits
- 5. Any subject that is currently on/requires oral, systemic or topical antibiotics, or is anticipated to require use during the course of the trial
- 6. Any subject that has vascular compromise requiring surgical intervention or has undergone vascular reconstruction or angioplasty less than 1 month prior to randomization. Any planned surgical procedures during the study participation
- 7. Serum Creatinine level >3.0 mg/dL
- 8. Hemoglobin A1c (HbA1c) >12%
- 9. Aspartate Aminotransferase (AST, GOT) and/or Alanine Aminotransferase (ALT, GPT) >3x the upper limit of normal
- 10. Acute active Charcot foot
- 11. The target ulcer is within 3 cm of any other ulcer.
- 12. Any subject that would be unable to safely monitor the infection status at home, and return for scheduled visits
- 13. History of immunosuppression or taking immunosuppressive agents including systemic corticosteroids, except stable daily doses of 5 mg/day or less for chronic conditions
- 14. Any subject with a life expectancy  $\leq 6$  months
- 15. Pregnancy, including a positive pregnancy test at Screening or Baseline, or lactation
- 16. Use of investigational drugs within 28 days prior to screening
- 17. History of concurrent condition that, in the Investigator's opinion, would jeopardize the safety of the subject or compliance with the protocol
- 18. Likely inability to comply with the protocol or cooperate fully with the investigator and site personnel
- 19. Known or suspected active abuse of alcohol, narcotics, or non-prescription drugs
- 20. Prior randomization in this clinical trial, or a previous Bisphosphocin study

# 6.1. Pregnancy and contraception guidance

Pregnancy and contraception guidance is provided in Appendix 1.

#### 6.2. Screen Failures

Screen failures are defined as subjects who consent to participate in the clinical study but are not subsequently entered in the study. A minimal set of screen failure information is required to ensure transparent reporting of screen failure subjects to meet the Consolidated Standards of Reporting Trials (COSORT) publishing requirements and to respond to queries from regulatory authorities. Minimal information includes demography, screen failure details, eligibility criteria, and any serious adverse event (SAE).

Individuals who do not meet the criteria for participation in this study may be rescreened. Rescreened subjects should be assigned a different screening number from their initial screening and can be rescreened up to two times.

# 7. TREATMENTS

Study treatment is defined as any investigational treatment(s) or placebo intended to be administered to a study subject according to the study protocol.

